2.3.1 Feasibility and usability metrics

The usability and feasibility of the adapted telehealth-delivered ACP intervention will be evaluated based on the following:

- a) Retention rate (percentage of patients who consented and completed the visit)
- b) Telehealth Usability Questionnaire (total average of >5 will be considered usable)

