7.2.2.17. Feasibility metrics

Feasibility metrics will be collected:

- Retention rate (percentage of patients consented to the study ultimately completing all study components) – primary metric
- Recruitment rate (percentage of patients who are approached and agree to enroll) will also be described

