We anticipate thematic saturation will be reached with this number of participants based on past similar research (i.e., the point at which no new data emerge).^{19,20} All interviews will be conducted and audio-recorded by study personnel and then transcribed by a professional transcription service. Two trained personnel ("coders") will extract and highlight themes from the transcripts. We will analyze the qualitative data using grounded theory and constant comparative methods, with coding to structure data into categories and create groups according to the broader issues or themes.⁴⁶ The themes will focus on EOL care as it relates to older patients with AML and MDS, barriers and challenges to ACP and MOLST completion, potential solutions and ideas, experience

with telehealth interventions, added values of the intervention, support and concerns for the proposed intervention, components of the intervention that are important to them, and their opinions about the intervention (e.g., delivery, format). We will keep an audit trail to establish trustworthiness. We will critically examine the data collection and analysis process, discuss emerging codes, and reach consensus on principal themes. These themes will be used to adapt the telehealth-delivered ACP intervention.

8.2.2. Analysis Plan for Aim 2

Quantitative analyses: We anticipate that our proposed sample size will be sufficient based on prior research²² and also published guidance on usability study.^{47,48} We will employ descriptive statistics to summarize the data. Feasibility will be defined based on the retention rate (percentage of patients consented to the study ultimately completing all study components); >80% will be considered feasible. Recruitment rate (percentage of patients who are approached and agree to enroll) will also be described. Usability will be defined based on the Telehealth Usability Questionnaire completed by patients; total average of >5 will be considered usable.^{49,50} We anticipate that about 20% of the participants will withdraw before post-intervention assessment due to death.⁵¹ With 20 patients enrolled, we anticipate at least 16 patients to be evaluable. When we estimate retention rate and usability, a 95% CI will span approximately +/- 25%. For example, if we observe 12/16 (75%) patients complete the tasks, the CI will be 51-90%.

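### The ±25% interval in Section 8.2.2, worked on 16 patients, fits neither endpoint: retention is defined over consented patients and usability is a mean score

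*Combined protocol and SAP*

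**What the plan says.** Section 8.2.2 of the combined protocol and SAP defines feasibility through the "retention rate (percentage of patients consented to the study ultimately completing all study components); >80% will be considered feasible". Section 7.2.2.17 gives the same definition and labels it the primary metric: "Retention rate (percentage of patients consented to the study ultimately completing all study components". Section 2.3.1 words the numerator differently: "Retention rate (percentage of patients who consented and completed the visit". That section attaches no threshold to retention; the >80% rule appears only in Section 8.2.2.

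Usability is an average score in both places where it is defined. Section 2.3.1 lists the "Telehealth Usability Questionnaire (total average of >5 will be considered usable", and Section 8.2.2 applies the same cut-off to the questionnaire as completed by patients.

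On expected losses, Section 8.2.2 says: "We anticipate that about 20% of the participants will withdraw before post-intervention assessment due to death". It continues: "With 20 patients enrolled, we anticipate at least 16 patients to be evaluable". One precision statement then covers both endpoints: "When we estimate retention rate and usability, a 95% CI will span approximately +/- 25" per cent. The illustration is: "if we observe 12/16 (75%) patients complete the tasks, the CI will be 51-90" per cent. Section 3.3 sets the Aim 2 target at 20 patients and allows up to 30 consents to cover screen failure and withdrawal.

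**The concern.** The 16 patients in the example are those left after the loss that retention is meant to measure. They belong in the numerator of retention, or near it, and not in its denominator. For usability the position is reversed: 16 is a sensible number of respondents, but the interval is for a proportion while the endpoint is a mean. So the sentence has the right type of interval with the wrong base for one endpoint, and a plausible base with the wrong type of interval for the other.

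Two things are at stake. The usability criterion has no applicable statement of precision. And an example built on 16 patients hides where the anticipated loss falls against the >80% cut-off once retention is computed as defined. The study's hypothesis is that the intervention is feasible and usable, so both criteria bear on its conclusion. The difference in numerator between Section 2.3.1 and the other two sections adds a further ambiguity about what is being estimated.

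**Working it through.** **Inputs.** From Section 8.2.2: 20 enrolled, about 20% lost to death, at least 16 evaluable, example 12/16, retention criterion >80%, mean usability criterion >5. From Section 3.3: up to 30 consents. The documents give no standard deviation for the questionnaire and do not name the interval method.

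**1. The plan's own figures.** The Wilson interval is [p + z²/2n ± z√(p(1−p)/n + z²/4n²)] / (1 + z²/n), with z = 1.96. For 12/16, p = 0.75 and z²/n = 0.240:
- centre = (0.75 + 0.120)/1.240 = 0.702
- half-width = 1.96 × √(0.01172 + 0.00375)/1.240 = 0.197
- interval = 50.5 to 89.8%, which rounds to the stated 51 to 90%

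The ±25% is the worst-case Wald half-width at n = 16: 1.96 × √(0.25/16) = 0.245. Both figures reproduce.

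**2. Retention on its defined base, 20 consented.**

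| Completers | Retention | Wilson 95% CI | Exceeds 80%? |
|---|---|---|---|
| 12/20 | 60% | 39 to 78% | No |
| 16/20 | 80% | 58 to 92% | No |
| 17/20 | 85% | 64 to 95% | Yes |

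The worst-case Wald half-width at n = 20 is 1.96 × √(0.25/20) = 0.219, against 0.245 at n = 16. The stated ±25% is therefore slightly conservative for retention.

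**3. Where the anticipated loss falls.** 20 × (1 − 0.20) = 16, and 16/20 = 80%, which is not >80%. The smallest passing count is 17. The chance of passing is the sum over k = 17 to 20 of C(20,k) pᵏ(1−p)²⁰⁻ᵏ:
- true retention 80%: 0.205 + 0.137 + 0.058 + 0.012 = 0.41
- true retention 85%: 0.65

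**4. Usability as a mean.** The 95% half-width is t(0.975, 15) × SD/√16 = 2.131/4 × SD = 0.53 × SD. For assumed SDs of 0.5, 1.0 and 1.5 this is 0.27, 0.53 and 0.80 score points. The SDs are illustrative only.

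**5. Effect of the denominator when more than 20 are consented.** If 20 patients complete everything and every consent counts in the denominator: 20/24 = 83% passes, 20/25 = 80% does not, and 20/30 = 67% does not. Whether post-consent screen failures count can therefore decide the result.

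**The case against.** The strongest reply is that the interval is correctly computed, errs on the cautious side for retention, and carries no design weight, because Section 8.2.2 justifies the sample size by prior research and published usability guidance. All of that stands and limits the harm. It does not make the figure apply to a mean score, or make 16 the denominator of a rate defined over consents.

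A reader might infer more than the documents support, in three ways:

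- **That the plan expects to fail its own criterion.** It does not say so. The loss is given as approximate and 16 as a minimum, so 17 or more is not excluded. In the other direction, the 20% covers deaths only, and the plan never equates being evaluable with completing every component. A feasibility bar may also reasonably sit at or above a cautious forecast. The 41% comes from placing true retention exactly at a strict cut-off; at 85% the chance is 65%. This is a boundary the example hides, not a contradiction.
- **That the two numerators give opposite feasibility verdicts.** Section 2.3.1 states no retention threshold. The >80% rule is tied only to completion of all components, so the operative definition can be identified and Section 2.3.1 needs only to be brought into line.
- **That the literal wording settles the place of screen failures.** Patients consented can be read to include them, but the plan also speaks throughout of 20 patients recruited or enrolled. This is a design choice for the sponsor.

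**Conclusion.** The point holds as a mismatch between a correctly calculated figure and the endpoints it is attached to; it is not a calculation error. For retention, 12 completers are 60% of 20 rather than 75% of 16, while the effect on worst-case width is small (21.9 against 24.5 points). For usability, the plan gives no applicable precision. On a base of 20, the approximate 20% loss falls at 80%, and 17 completers are needed to exceed the criterion. The retention figures assume that 20 patients form the denominator; the passing probabilities also assume independent outcomes at the stated true rates. The usability half-width assumes 16 respondents and an SD that the documents do not supply. The correction is worth making before Aim 2 is analysed, but it does not call the sample size into question.

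**What to change.** In Section 8.2.2, replace the precision sentence and its example with:

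> Retention will be reported with a Wilson 95% CI on its defined denominator (with 20 patients: 16/20 = 80%, 58 to 92%; 17/20 = 85%, 64 to 95%; at least 17 of 20 are needed to exceed 80%). Usability will be reported as the mean Telehealth Usability Questionnaire score with a t-based 95% CI (half-width 0.53 × SD at n = 16).

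In Section 2.3.1, change the retention numerator from completion of the visit to completion of all study components, so that it agrees with Sections 7.2.2.17 and 8.2.2.

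Separately, the sponsor should state before analysis whether patients who screen-fail after consent count in the retention denominator. This review does not choose for them.

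The cost is wording in two sections plus that one decision. Sample size, procedures, data collection and the >80% and >5 criteria are unchanged. The decision on screen failures is more than editorial, since it can change the feasibility verdict, and so it should be fixed before the results are known.

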9.0 Data Management

9.1. Data Collection Table

9.1.1. Aim 1

a) Patient

	Eligibility and consent form	Assessment
Informed Consent	X	
Demographics		X
Clinical and Cancer Characteristics		X
Cancer Health Literacy (CHLT-6)		X
Qualitative Interview		X
Disease Understanding		X

b) Caregiver (if applicable)

	Eligibility and consent form	Assessment
Informed Consent	X	
Demographics		X
Cancer Health Literacy (CHLT-6)		X
Qualitative Interview		X
Disease Understanding		X

c) Oncology and Palliative Provider

	Eligibility and consent form	Assessment
Informed Consent	X	
Demographics		X
Qualitative Interview		X

9.1.2. Aim 2

a) Patient

	Eligibility and consent form	Baseline Assessment	Post-Intervention Assessment (within 4 weeks of the telehealth visit and up to 12 weeks)
Informed Consent	X		
Demographics		X	
Clinical and Cancer Characteristics		X	
Qualitative Interview			X
Activities of Daily Living (ADL), Instrumental Activities of Daily Living (IADL), Fall History		X	
Patient Health Questionnaire (PHQ-9), General Anxiety Disorder-7 (GAD-7), Distress		X	X
Nutritional Status		X	
OARS Medical Social Support		X	
Cognition (BLESSED)		X	
Health Care Communication Questionnaire (HCCQ), Heard and understood question			X
Therapeutic alliance Human Connection Survey			X
Cancer Health Literacy (CHLT-6)		X	
Telehealth Usability Questionnaire (TUQ)			X
Acceptability			X
ACP engagement survey		X	X
Peaceful acceptance of illness			X
Goal concordant care			X
Functional Assessment of Cancer Therapy-Leukemia (FACT-Leu)		X	X
Disease Understanding		X	X

b) Caregiver (if applicable)

	Eligibility and consent form	Baseline Assessment	Post-Intervention Assessment (within 4 weeks of the telehealth visit and up to 12 weeks)
Informed Consent	X		
Demographics		X	
Patient Health Questionnaire (PHQ-9), General Anxiety Disorder-7 (GAD-7), Distress		X	X
Qualitative Interview			X
Cancer Health Literacy (CHLT-6)		X	
Health Care Climate Questionnaire (HCCQ), Heard and understood question			X
Telehealth Usability Questionnaire (TUQ)			X
Caregiver Quality of Life Index-Cancer		X	X
Disease Understanding		X	X

c) Oncology provider

	Eligibility and consent form	Baseline Assessment	Post-Intervention Assessment (within 4 weeks of the telehealth visit and up to 12 weeks)
Informed Consent	X		
Demographics		X	
Qualitative Interview			X
Disease Understanding			X
Acceptability			X
Provider confidence survey		X	X

9.2. All hardcopy research records will be stored onsite in the URMC, in locked research files at the WCI. The Cancer Center is secured with electronic key cards. Offices within the Cancer Center are again secured by key and data is kept in locked file cabinets. Electronic research records are stored on the URMC's password secured and firewall protected networks. These are the same methods of security used for patient medical records. For audio-recordings, these will be uploaded to Box within a week of the interview and deleted from the audio recorder. All study

data will be kept for a period of 7 years after the study and all reports and publications are complete.

9.3. All data collected for the current study will be used in post hoc analyses as appropriate. Data will not be used for future studies without prior consent of the patient. The patient's individual research record will not be shared with their treating physician, unless they provide consent or the patient's treating physician is a study physician, in which case they will have access to study data as a study co-investigator. Overall study results will be presented to participants, faculty and staff at the URMC after completion of the study. Study results will be presented at professional meetings and published.

9.4. The study coordinator will assign a numerical study ID to each participant once they have signed the consent form (chronologically based on the data they signed consent i.e., 001, 002, 003...). All study forms and questionnaires will use this number and the participant's first, middle, and last initials as identifiers, to ensure data integrity. Other identifying information will not exist on these forms. A complete list of study participants with study ID, name, and contact information will be maintained separately. This linkage information will only be accessible to the study coordinator, study investigators, and the individuals responsible for maintaining the database.

9.5. Additionally, data on the socio-demographics, clinical, and cancer and treatment characteristics will be collected and managed by the research teams at URMC using REDCap electronic data capture tools hosted at URMC.⁵² We will also evaluate the medical records for clinical characteristics and outcomes, and utilize REDCap to collect and manage this information.

9.5a. URMC provides the following information on the REDCap program: "Vanderbilt University, in collaboration with a consortium of institutional partners, has developed a software toolset and workflow methodology for electronic collection and management of research and clinical trial data, called REDCap (Research Electronic Data Capture). The REDCap system is a secure, web-based application that is flexible enough to be used for a variety of types of research. It provides an intuitive interface for users to enter data and real time validation rules (with automated data type and range checks) at the time of data entry. REDCap offers easy data manipulation with audit trails and functionality for reporting, monitoring and querying patient records, as well as an automated export mechanism to common statistical packages (SPSS, SAS, Stata, R/S-Plus). Through the REDCap Consortium, Vanderbilt has disseminated REDCap for use around the world. Currently, over 240 academic and non-profit consortium partners on six continents with over 26,000 research end-users use REDCap.⁵³

9.5b. According to the Clinical and Translational Science Institute (CTSI), REDCap is supported with the following means. "The *CTSI Informatics Core*, a unit of the SMD *Academic Information Technology (AIT) Group*, will serve as a central facilitator for data processing and management. REDCap data collection projects rely on a thorough study-specific data dictionary defined in an iterative self-documenting process by all members of

the research team, with planning assistance from the *AIT-CTSI Informatics Core*. The iterative development and testing process results in a well-planned data collection strategy for individual studies.”⁴⁶

9.5c. The CTSI states that regarding security, “REDCap servers are housed in a local data center at the University of Rochester and all web-based information transmission is encrypted. REDCap was developed in a manner consistent with HIPAA security requirements and is recommended to University of Rochester researchers by the URMC Research Privacy Officer and Office for Human Subject Protection.⁵³

10.0 Risks/Benefits

10.1. Risks

There is potential loss of confidentiality associated with participation in the proposed study. In terms of loss of confidentiality, quantitative data from participants will need to be stored. Though rigorous and well-tested data safety and security guidelines will be observed, there is still a chance that confidentiality could be breached and sensitive medical information could become known to persons outside the research team.

10.2. Benefits

There are no anticipated benefits to the participants.

10.3 Payments and Costs

Patients and caregivers participating will be paid \$10 Wegmans gift cards. For Aim 1, participants will receive the Wegmans gift cards immediately following the interviews. For Aim 2, participants will be paid for completion of the post-intervention assessment. Oncology providers will not be reimbursed for their participation.

